People with fear of confined spaces may become anxious during an MRI. Those with back problems may have back pain or discomfort from lying in the scanner. The noise from the scanner is loud enough to damage hearing, especially in people who already have hearing loss. Subjects will be fitted with hearing protection. Subjects will be instructed to let us know right away should the hearing protection come loose during the scan. Subjects will also be instructed to notify the investigators if they have hearing or ear problems. Subjects will be asked to complete an MRI screening before having the MRI. There are no known long-term risks of MRI scans.

Risks and discomforts associated with an intravenous line:

The risks of an intravenous catheter include bleeding, infection, or inflammation of the skin and vein, with pain and swelling.

Risks and discomforts associated with naloxone:

Naloxone is an opiate antagonist and is clinically available and commonly used to reverse the adverse effects of opiates, such as remifentanil. Naloxone does not produce respiratory depression, psychotomimetic effects or pupillary constriction. Naloxone has not been shown to produce tolerance or cause physical or psychological dependence. In the presence of opioid dependence, naloxone may produce withdrawal symptoms. While the mechanisms of action of naloxone is not fully understood, most evidence suggests that naloxone antagonizes the opioid effects by competing for the μ , κ , and σ opiate receptor sites in the CNS, with the greatest affinity for the μ receptor. Following parenteral (outside the intestine) administration, naloxone is rapidly distributed in the body and readily crosses the placenta. Plasma protein binding occurs

but is relatively weak. Plasma albumin is the major binding constituent but significant binding of naloxone also occurs to plasma constituents other than albumin. Naloxone is metabolized in the liver, primarily by glucuronide conjugation with naloxone-3-glucoronide as the major metabolite. The serum half-life ranges from 30 to 81 minutes (mean 64 ± 12 minutes).

Naloxone is generally thought to be well tolerated and safe. Most of the potential risks associated with naloxone are specific to its precipitating opiate withdrawal and do not apply to its use when patients have no opiates in their system, such as is the case with our study. The most common side effects that have been reported when naloxone is given post-operatively are nausea and vomiting, reversal of pain relief, agitation, and increased or decreased blood pressure. Adverse cardiovascular effects have occurred most frequently in postoperative patients with preexisting cardiovascular disease or in those receiving other drugs that produce similar adverse cardiovascular effects. In experimental studies in subjects not taking opiates (as in our study), the only reported side effects are dry mouth and dizziness. It is important to note that experimental and clinical studies with naloxone have been successfully conducted since the 1960's.

Risks and discomforts associated with heat pain stimuli

Several different sites are stimulated in order to minimize sensitization of the skin. However, reddening of the skin might occur. This is transient and disappears after termination of the testing. The heat stimuli, which are of moderate to strong intensity, will not damage the skin. Heat pain stimulation has been used extensively without any long-term adverse effects [37, 40, 46].

Risks and discomforts associated with brushing and compression stimuli

There are no known risks of the gentle brushing. Pressure stimuli may be uncomfortable to some participants, but the pressure will be lower than a standard blood pressure cuff and thus familiar to all participants. Repeated inflation could dislodge any active blood clots in the participant's leg, so all participants will be checked during medical screening to ensure they do not have any clinical signs of clots present.

Risks and discomfort associated with physiological monitoring

There is no medical risk associated with physiological monitoring. The belts used for respiration monitoring can feel uncomfortable to certain individuals when first attached but this usually subsides.

Risks for screening and questionnaires

We have included a number of validated questionnaires to assess variations across individuals. Some of these items include sensitive questions about one's psychological and emotional state. Participants will be informed that they can skip any questions they do not wish to answer, and that participation is voluntary.

8. Subject Safety Monitoring

Participants will be monitored by the study investigators during all study visits for study outcomes and adverse events. All subjects will be instructed about, and receive practice with, each test before they begin to perform it and, before a test is formally administered, adequate comprehension of the instructions for each test will be insured by the test examiner.

During an assessment, testers are usually in the room with the subject or in the room just outside the fMRI room. Study staff will monitor individuals during participation and subjects will be encouraged to tell experimenters of any discomfort. If apparatus, etc., cannot be adjusted to relieve discomfort, the experiment will be stopped. Subjects may withdraw at any time.

During MRI scanning, subjects will be given a call button and instructed to use it in case of emergency or if the subject feels any discomfort in the scanner. Throughout the scan session, verbal contact with the subject will be maintained from the control room via an intercom device.

Participants can withdraw from this study at any time and for any reason without loss of benefits or privileges to which they are otherwise entitled or prohibition from enrolling in other clinical protocols. Investigators can remove a participant from the study if an exclusionary condition develops, if the investigator believes that continuation is not in the best medical interest of the subject, or if the subject is unable to comply with study requirements. Sessions

may also be terminated early due to factors that do not directly influence subject safety, such as technical difficulties (e.g. equipment malfunction, computer issues), if schedule conflicts arise (e.g. participant arrives late or needs to leave early; MRI scanner availability is not sufficient to complete the experiment; delays in Clinical Center waiting time, time to process lab orders and lab results). When sessions are terminated early, participants may be asked whether they wish to reschedule. If participants end a session due to discomfort, they will be asked whether they want to continue with other phases of the study, and/or participate in other sub-studies in the protocol.

A. Withdrawal Criteria

Participants can withdraw from this study at any time and for any reason without loss of benefits or privileges to which they are otherwise entitled, or prohibition from enrolling in other clinical protocols. Investigators can remove a participant from the study if an exclusionary condition develops, if the investigator believes that continuation is not in the best medical interest of the subject, or if the subject unable to comply with study requirements.

B. Criteria for Stopping study

In all subjects, procedures will be stopped if requested by participants or if the investigators feel it is in the best interest of the participant.

9. Outcome Measures

a. Primary outcome measures

The primary outcome is the change or difference in pleasantness rating between post-drug and pre-drug of light stroking.

b. Secondary outcome measures

The secondary outcomes include change or differences between post-drug and pre-drug ratings for 1) pleasantness and/or intensity of deep pressure 2) unpleasantness and/or intensity of cutaneous heat pain.)

c. Tertiary outcome measures

- 1) Determine the role of mood or anxiety changes in mediating the effect of endogenous opioids on these perceptual measures; 2) Determine changes in the brain activation related to these effects.

10. Statistical Analysis

a. Analysis of data/ study outcomes

Testing for normal distribution

All data will be assessed for normality of distribution using the Shapiro Wilk W test. A significant W statistic indicates that the hypothesis of a normal distribution should be rejected, i.e. a significant W indicates skewed data. If the data is skewed the data transformation method will be chosen based on the distribution (Box-Cox method) of the dependent variable. The resulting transformed data will be analyzed with parametric statistics. In the descriptions below we will describe the parametric statistical tests. If data transformation does not work, non-parametric tests will be applied.

Behavioral Data

All behavioral data will be analyzed using SPSS or similar statistical package. A significance level of $p < 0.05$ will be adopted for all analyses.

For the primary and secondary outcomes, we will use paired t-test to evaluate the drug effect. To determine whether the effect of drug on touch pleasantness is mediated by mood, we will use Wager & Lindquist's Multilevel Mediation and Moderation (M3) Toolbox. In the analysis, the dependent variables are the sensory ratings, the independent variable is the drug and the mediator variable is mood.

MRI data will be analyzed using standard brain imaging packages such as FSL or AFNI. For the initial analysis, the individual performing the analysis will be blinded. Whole brain analysis will be the first analysis performed followed by analysis looking at individual activations (parameter

estimates) in regions of interest including the insula, cingulate cortex and orbitofrontal cortex. These activations will be used to conduct a mediation analysis of these brain areas in mediating the effect of drug on touch pleasantness ratings. In this analysis, the dependent variables are the perceptual ratings, the independent variable is the level of stimulus and the mediator is the BOLD activation in the brain area of interest (ROI).

b. Power analysis

In order to yield meaningful statistical analyses of the psychophysical data, and specifically for our primary outcome measure, we estimate that the sample size required to complete the study would be 24 healthy participants. G*Power (<http://www.gpower.hhu.de>) was used to compute the necessary sample size. We used a Cohen's effect size $d = 0.61$ based on the means and standard deviations of pleasantness rating changes in our previous study of naloxone versus saline [9], statistical power of 80%, and Type I error probability $\alpha=0.05$. The effect size of 0.61 is clinically important for the pleasantness rating outcome. We expect a 20% dropout rate of participants based on prior NIH studies. Thus, we will enroll up to 30 participants and dropouts will be replaced.

11. Human Subjects Protection

a. Subject selection

Accrual will be equitable among the participants eligible for this study.

b. Justification for exclusion of children

The current study constitutes initial research into the affective mechanisms of light stroking and deep pressure touch and involves procedures such as intravenous drug infusion that are likely to not be well tolerated by children, with no particular benefit to them. In addition, there is evidence that affective touch perception differs by age, both in perception and in brain processing, with children and older adults differing from young and middle-aged adults [47, 48] which would add significant variability to the data. A separate, age-specific study in children is thus warranted and preferable and children will not be included in the current study.

c. Justification for exclusion of other vulnerable subjects

Participants who do not speak English will not be enrolled because our complete set of questionnaires is only validated in English.

Individuals without consent capacity will be excluded because the research question can be answered by enrolling only adults who can consent, and participation does not offer the potential for important clinical benefit. Therefore, the risk outweighs the benefit in this population.

Pregnant women and lactating women are excluded because pregnancy and lactation significantly alter a women's hormonal profile and hormones affect touch processing [49, 50], and because MRI is contraindicated for pregnancy.

Individuals weighing more than 550 lbs. will be excluded because of the weight limit of the MRI scanner.

Because older adults have elevated pain thresholds for brief pain stimuli [51] and there is no evidence that their discriminative functions are unchanged, we are excluding people over 50 years of age.

We will include only right-handed individuals because of increased variability in the lateralization of functions in left-handers, including asymmetries in representations of sensory function [52].

d. Justification for sensitive procedures

N/A

e. Safeguards for vulnerable populations and sensitive procedures

For all fMRI experiments, pregnant women will be excluded from participation due to the unknown effects of the high magnetic field on the developing fetus.

While NCCIH employees are excluded from participation, NIH employees and staff may also be considered vulnerable. Protections for employees and staff participating in this study

include 1) assuring that the participation or refusal to participate will have no effect, either beneficial or adverse, on the subject's employment or position at the NIH, 2) giving employees and staff who are interested in participating the "NIH Information Sheet on Employee Research Participation" prior to obtaining consent, and 3) assuring that there will be no direct solicitation of employees or staff. This study collects sensitive information on drug use and alcohol use and specific medical diagnoses. The PI will train study staff regarding obtaining and handling potentially sensitive and private information about co-workers through staff discussions and written branch/section procedures. Prior to enrollment, potential participants will be informed that this sensitive information will be in their NIH medical record.

12. Anticipated Benefit

The study does not offer direct benefit to participants. However, findings from these studies will contribute to a mechanistic understanding of affective touch, with potential implications for chronic pain.

14. Consent Documents and Process

a. Consent procedures

Informed consent for this study will be obtained in-person at the initial visit or during a separate visit prior to Session 1, after the initial inclusion criteria have been met via the telephone interview and prior to the medical exam or any experimental procedure. The participants will have an opportunity to carefully review the consent and ask questions regarding this study prior to signing, and they will be informed that they may withdraw from the study at any time without prejudice to themselves. The consent procedures will be conducted in a private room by a qualified study investigator. All participants will receive a verbal explanation in terms suited to their comprehension of the purposes, procedures and potential risks of the study and of their rights as research participants. Participants will have the opportunity to carefully review the written consent form and ask questions regarding this study prior to signing. NIH employees will

not be consented by a coworker.

b. Consent documents

The consent form contains all required elements. The consent document is submitted with this protocol.

15. Data and Safety Monitoring

a. Data and safety monitor

The Principal Investigator will be responsible for monitoring data and safety.

b. Data and safety monitoring plan

The Principal Investigator is responsible for maintaining adequate clinical records documenting the medical history, condition and test results for each study participant throughout the study. Source documentation may consist of written or electronic records and supporting data maintained by the PI and/or the institution. The medical records for each participant shall document that informed consent was obtained prior to participation in the study.

[name] will review progress of the study annually. Adverse events data will be reviewed as they arise to ascertain whether or not there are safety concerns with study procedures.

c. Criteria for stopping the study or suspending enrollment or procedures

If there is any serious adverse event (SAE) related to the research, the study will halt until the adverse event and a plan to address the SAE has been resolved by the investigator, clinical director, and the IRB.

16. Quality Assurance

a. Quality assurance monitor

The Principal Investigator is responsible for monitoring the quality assurance of this protocol.

b. Quality assurance plan

On a monthly basis, the PI will review all regulatory and patient information with the study team to ensure data and study integrity are maintained. Data collected on prepared questionnaire forms will be entered into a database against the original source and checked by someone other than the initial person entering data. In addition, this protocol will undergo audits by the QA audit committee as outlined in the NINDS QA Standard Operating Procedure. For studies greater than minimal risk, auditing is conducted in the first year followed by audits q3 year (every third year). The purpose of the QA audit is to assess compliance with applicable regulatory requirements and good clinical practice guidelines, as well as to provide recommendations for improving the management of clinical research data.

17. Reporting of Unanticipated Problems, Adverse Events and Protocol Deviations

Reportable events for this protocol will be tracked and reported in compliance with policy 801.

18. Alternatives to Participation

Subjects do not receive any treatment in this study or forego any treatment in order to participate in this study. The alternative, therefore, is not to participate.

19. Privacy

All research activities will be conducted in as private a setting as possible.

20. Confidentiality

a. For research data and investigator medical records

- We will actively protect confidentiality of the subjects and the data at each step. All medical records and subject data will be kept confidential and will only be reviewed by the participating investigators. Data will be de-identified and stored using codes that we assign. De-identified data will be kept in encrypted password-protected NCCIH computers in rooms that are locked

when not occupied. Hard copy records/data will be kept in locked cabinets in rooms that are locked when not occupied. Only study investigators will have access to the data.

- Research staff will be trained by the PI to respect the privacy and confidentiality of NIH employees and staff, especially with regard to sensitive, private information. All data will be de-identified and personnel will not view data alongside identifying information, which will reduce the possibility that lab personnel would be able to associate sensitive information with individuals. The lab will discuss professionalism and confidentiality, and if lab personnel are acquainted with any potential participants, a different investigator will interact with that participant.

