Protocol Title: Sensory and Opioid Mechanisms of Affective Touch

Abbreviated Title: Affective Touch

Protocol Number: 17-AT-0075

Date of This Submission/Version: 07/27/2020, Version 1.7

Principal Investigator

M. [name]	NCCIH	[name]	[contact]	[contact]
----------------------------	-------	---------------------	--------------	-----------------------

Human Research Protections Program Investigator and Staff Training:

For this protocol, the following "Just in time" human subjects protection training courses are required for investigators and staff:

None

Total requested accrual

30 Healthy Volunteers

Project Uses Ionizing Radiation: No Yes

IND/IDE No Yes

Durable Power of Attorney No Yes

Multi-institutional Project No Yes

Data and Safety Monitoring Board No Yes

Technology Transfer Agreement No Yes

Samples are being stored No Yes

Flesch-Kincaid reading level of consent form: 8.3

Précis:

Objective: Our recent pilot study found evidence suggesting that blocking endogenous opioid release increases the pleasantness associated with having the skin stroked. Deep pressure touch (observed in hugs and massage) also typically conveys a sense of pleasantness. This increased pleasantness contrasts with evidence that blocking endogenous opioid release increases pain. The current study will examine the role of endogenous opioids in the pleasantness of light skin stroking and deep pressure touch, and contrast it with their role in the unpleasantness of a painful heat stimulus. Further, it will examine the neural basis of observed perceptual changes, using fMRI. This study constitutes the first study of the K99 phase of a K99/R00 grant application recently submitted to NCCIH by [name].

Study Population: 30 healthy participants will be enrolled in the study.

Design: Participants will receive intravenous saline or intravenous naloxone on separate days to investigate the effect of mu-opioid antagonism on the intensity and pleasantness of superficial and deep affective touch and the intensity and unpleasantness of cutaneous heat pain. Using a double-blind cross-over design, functional Magnetic Resonance Imaging (fMRI) will be conducted during sensory testing before and after the infusion of each drug to examine the neural mediation of opioid effects on touch perception. Ratings of mood, anxiety, pain intensity, pleasantness/unpleasantness, wanting and liking will also be collected throughout the study session.

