A parallel system to the skin's C-LTMRs may be present in form of unmyelinated pressure-sensitive afferents identified in skeletal muscle and tendon of cat [14] which may mediate the pleasurable experience of deep pressure touch. In humans, deep pressure touch has been shown to reduce anxiety [15], pain and unpleasant affect [16]. For the beneficial effects of massage therapy [17], the exertion of moderate pressure (compared to light pressure or vibration) is necessary and leads to greater reduction of stress and anxiety as well as higher pleasantness ratings [18]. Both light skin stroking and deep pressure touch are components of numerous complementary health techniques which significantly reduce depression, stress, and pain [19, 20]. By including deep pressure touch as a condition in our current study we aim to investigate, through blockage of the endogenous opioid system (naloxone administration), if the pleasantness of light skin stroking and the pleasantness of deep pressure touch are both similarly dependent on endogenous opioids, and whether mood mediates this effect.

Endogenous opioids are central to the perception of pleasure and reward (wanting and liking) which serve as crucial balancing systems for pain and associated psychiatric conditions. To address the question of pain modulatory properties of the endogenous opioid system, specifically on the affective component of pain, we include an experimental heat pain condition in our study and administer an opioid blockade (naloxone). Previous studies of the effect of blocking opioid

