receptors on pain perception have produced conflicting results: no effect on pain [21-24], increased pain following high dose and decreased pain at low dose naloxone[25-28]. The same contradictory findings are true for several rodent studies [29-32]. To our knowledge, the ratings in the human studies were all unitary measures of pain intensity. However, a more recent study on this topic [33] utilized rating systems for both pain unpleasantness and pain intensity allowing the authors to differentiate the affective component of pain. The opioid blockade significantly increased pain unpleasantness ratings of experimental pain but the pain intensity ratings remained unaffected [33]. Our aim is to replicate this finding and add to it brain imaging data (fMRI) to characterize the brain areas associated with producing this dichotomized pain perception. By deciphering this neuronal process we could potentially also understand how mood can alter pain unpleasantness independent of pain intensity [34], if understood these components strengthen therapeutic strategies for treatment of chronic pain using mood altering therapies.

2. Study Objectives

Hypothesis 1 (primary outcome): Participants will experience a significant increase in the pleasantness but not intensity of cutaneous brushing and deep skin/muscle pressure after administration of naloxone (compared to saline).

Hypothesis 2 (secondary outcome): Participants will experience a significant increase in the unpleasantness but not intensity of cutaneous heat pain after naloxone administration.

Hypothesis 3 (secondary outcome): The effect of endogenous opioids on perception will be partially mediated by changes in mood, with negative mood increasing the pleasantness of pleasant touch and increasing the unpleasantness of pain.

Hypothesis 4 (secondary outcome): Stimulus-evoked neural activations will be modulated by naloxone administration, with preferential effects in cingulate cortex and insula.

3. Subjects

a. Description of study populations

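### Two comparative aims, stroking versus deep pressure and touch versus heat pain, have no planned test: Section 10a tests the drug effect separately for each outcome

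*Combined protocol and SAP*

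**What the plan says.** Two places state an aim that compares drug effects between stimuli.

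- Section 1 (Introduction and Background) gives the reason for the deep-pressure condition: to find out "if the pleasantness of light skin stroking and the pleasantness of deep pressure touch are both similarly dependent on endogenous opioids".
- The Précis, under Objective, says the study will examine the opioid role in the two kinds of touch "and contrast it with their role in the unpleasantness of a painful heat stimulus".

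The rest of the plan works one stimulus at a time. Section 9a: "The primary outcome is the change or difference in pleasantness rating between post-drug and pre-drug of light stroking". Section 9b lists the secondary outcomes as "pleasantness and/or intensity of deep pressure 2) unpleasantness and/or intensity of cutaneous heat pain". The four hypotheses in Section 2 likewise contain no comparison between stimuli.

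Section 10a then says: "For the primary and secondary outcomes, we will use paired t-test to evaluate the drug effect". The mood mediation model is described as one in which "the dependent variables are the sensory ratings, the independent variable is the drug and the mediator variable is mood". The brain mediation model uses stimulus level and BOLD activation. Neither has a term for type of stimulus. The plan gives no drug-by-stimulus contrast, no confidence interval for a difference between drug effects, and no margin for calling two effects similar.

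**The concern.** Whether two stimuli depend on opioids alike is a question about the difference between two drug effects. A separate test of each effect does not answer it. One result below 0.05 and one above does not show that the effects differ. Two results below 0.05 do not show that they are similar.

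At stake is what may be concluded about the deep-pressure condition, and about touch against pain when one of those tests is null. Any statement of alike or different drawn from the planned output would carry no controlled error rate. Yet the direct comparison is available. Every participant rates every stimulus block before and after infusion in both sessions, on one hedonic scale from -100 to 100 (Section 4d).

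**Working it through.** **The plan's own figure.** Section 10b gives d = 0.61, 80% power, alpha 0.05 and n = 24. The exact power of a two-sided paired t-test is 0.798 at n = 23 and 0.816 at n = 24, so 24 reproduces. With 20% dropout, 24/0.8 = 30, as stated. This powers one drug effect at a time.

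**Set-up for the comparison.** For each participant and stimulus let D = (post - pre on naloxone) - (post - pre on saline). Assume equal SDs of D for stroking and pressure, with D in SD units, and let ρ be the correlation between the two D values. The documents do not give ρ, so a range is shown. The contrast D_stroking - D_pressure has SD s = √(2(1 - ρ)) and standardized effect (d1 - d2)/s.

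**How often separate tests disagree when the true effects are equal (both 0.61).** At ρ = 0 this follows directly: 2 × 0.816 × (1 - 0.816) = 0.30. The other values come from simulation at n = 24. The 90% CI half-width is 1.714 × s/√24.

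| ρ | s | exactly one test significant, equal effects | contrast: power for 0.61 v 0 | contrast: power for 0.61 v 0.305 | 90% CI half-width (SD) |
|---|---|---|---|---|---|
| 0 | 1.414 | 30% | 53% | 17% | 0.495 |
| 0.5 | 1.000 | 22% | 82% | 30% | 0.35 |
| 0.75 | 0.707 | 15% | 98% | 53% | 0.25 |
| 0.9 | 0.447 | 10% | over 99% | 89% | 0.16 |

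In every row the direct contrast falsely declares a difference in about 5% of trials.

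**Why two significant tests do not show similarity.** Suppose, as an assumption, that one effect is 0.61 and the other half of it, 0.305. The second test has power 0.30 at n = 24. At ρ = 0 both are significant in 0.816 × 0.30 = 0.24 of trials, although one effect is twice the other.

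**What an equivalence claim could achieve.** Suppose the effects are truly equal and the 90% CI must lie within an assumed margin of 0.5 SD. The claim succeeds in about 9% of trials at ρ = 0 and 54% at ρ = 0.5 (simulated). With a margin of 0.305 SD, success is about 0% and 2%.

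**Touch against pain.** Section 2 predicts that naloxone raises touch pleasantness and raises pain unpleasantness, which are opposite signs on the shared scale. If the effects were +0.61 and -0.61 with ρ = 0, the signed contrast would have standardized effect 1.22/1.414 = 0.86 and power about 98%. A negative ρ would lower this.

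**The case against.** The strongest reply is that the formal plan is coherent. The section headed Study Objectives has four hypotheses, none comparing drug effects between stimuli, and paired t-tests match them and the outcomes in Section 9. The comparative wording is one clause in the Précis and one sentence of background, and the registry précis in Attachment 3 leaves the contrast out. Being similarly dependent can also be read loosely as both rising under naloxone, which separate tests do address. This stands as a limit on the point. It does not remove the gap, because Section 1 offers the comparison as the reason for including deep pressure.

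A reader might infer that the investigators intend to compare p-values. The documents do not say so. They name no method, and an informal comparison of effect sizes is equally possible, though it would have no error rate either.

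A reader might also infer that touch against pain cannot be answered as planned. That goes too far. Two significant effects of opposite sign would already show that naloxone moves the two ratings differently. The gap opens when one test is null, which is realistic since Section 1 calls earlier pain findings conflicting.

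Finally, the direct contrast is weak for stroking against pressure unless ρ is about 0.5 or higher and one effect is near zero. That is true, and is a reason to report an interval and limit the claim.

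**Conclusion.** The point holds as a gap between two stated aims and the analysis plan. A reader might take it to mean that a numbered hypothesis lacks its test or that the primary result is compromised. Neither follows: the primary outcome, its test and n = 24 stand.

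The size is 10% to 30% discordant results between stroking and pressure when their true effects are equal at d = 0.61, against 5% false differences from the direct contrast. This rests on equal SDs, normal ratings, two-sided tests, 24 completers and ρ between 0 and 0.9. The higher ρ is, the smaller the problem and the better the contrast performs. Adding the contrasts is a worthwhile, inexpensive improvement.

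**What to change.** Add one paragraph to Section 10a, as secondary analysis:

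1. Define D as above on the hedonic scale, for named stimulus levels. Section 4d has two brushing speeds, two pressures and two heat levels, so the levels must be chosen in advance; for example slow brushing, the pleasant pressure and painful heat.
2. Report D_stroking - D_pressure with a paired t-test and 95% CI. State that a difference will be claimed only from this contrast, and that two significant separate tests will not be reported as similarity. Report the CI in place of an equivalence claim unless a margin is fixed before unblinding.
3. For touch against pain, define touch (stroking, pressure or their average). Report the signed contrast D_touch - D_heat as a test of whether naloxone moves the hedonic ratings differently, with no equivalence claim. If the question is the size of opioid dependence, compare D_touch with -D_heat; a signed contrast would reject even for effects of equal size and opposite direction.

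Alternatively, withdraw the two comparative statements from the Précis and Section 1.

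The cost is the paragraph and a few extra contrasts on data already collected, with no change to the primary test or sample size. The downside is that the stroking-pressure result may be inconclusive, with a 90% CI half-width of about 0.5 SD at correlation 0 and 0.35 SD at 0.5.
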